5.4.1 Discontinuation from Study Treatment

Subjects who discontinue study treatment will still continue study follow-up procedures. Investigators are encouraged to assess all subjects according to the study protocol even after discontinuation from study treatment.

- Investigators can discontinue subjects from study treatment in case of unacceptable toxicity, non-compliance, disease progression requiring alternative therapy, or if the investigator determines it is in the subject's best interest.
- Astex Pharmaceuticals may require that a subject is discontinued from treatment for safety reasons or for noncompliance.

In all cases, the reason(s) for discontinuation from study treatment must be recorded in the source document and on the relevant page of the subject's case report form or electronic case report form (CRF/eCRF).

It is important to obtain protocol-specified follow-up information on any subject discontinued from study treatment. Section 10.0 describes follow-up for AEs. Subjects should be followed for survival information until death, withdrawal of consent, or termination of the clinical trial. Safety should be followed for 30 days after the last dose of study treatment, or until the subject starts alternative anti-leukemia treatment for AML (except for hydroxyurea as specified in Section 7.4.1), whichever happens earlier (see Section 10.4). Collection of AEs and concomitant medications may also continue until the decision is made to permanently discontinue study treatment. Subjects in the BSC group will be considered to be on study treatment until they have disease progression.

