11.6.2.1 Event-free Survival (EFS)

EFS is defined as the number of days from randomization to the earliest of disease progression, treatment discontinuation, start of alternative anti-leukemia therapy (except for HCT), or death.

Disease progression is defined as earliest occurrence of one of the following:

- For subjects with CR, CRh, CRi, or CRp, the confirmed (at least 2 PB samples at least 1 week apart) appearance of ≥5% leukemic blasts in PB, OR ≥5% leukemic blasts in the BM.
- For all other subjects, when PB or BM shows evidence of continued increase in blasts % that necessitates alternative therapy.

EFS will be displayed using a Kaplan-Meier estimate and will be compared between the two treatment groups using a log-rank test stratified by the randomization stratification factors. EFS time will be censored on the last date the subject is known to be alive without an EFS event.

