1.0 INTRODUCTION

This Statistical Analysis Plan (SAP) is based on SGI-110-06 protocol version 4.0, dated 29 October 2018. Based on data from 278 randomly assigned subjects, the Data Monitoring Committee (DMC) recommended stopping further enrollment into the trial based on futility analysis that indicated the trial was unlikely to show superiority of guadecitabine over treatment choice (TC) for overall survival (OS). Consequently, the study was closed to further enrollment in September 2018 (protocol amendment 4).

Analyses and statistical reporting for SGI-110-06 will be conducted by Astex Pharmaceuticals Biostatistics department with the interim analysis results as reported by the study's DMC. The analyses specified in this document supersede the high-level analysis plan described in the protocol.

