7.3.2.1 Event-Free Survival

Event-free survival (EFS) is defined as the time, in days, from the subject randomization date to the earliest of treatment discontinuation (for reasons other than initiation of HCT), start of alternative anti-leukemia therapy (other than HCT), or death.

In the absence of any of these events at the time of analysis, event-free survival time will be censored on the last date the subject is known alive. Subjects who do not have post-baseline information will be censored at the date of randomization.

EFS curves will be estimated using the Kaplan-Meier method and formally compared between the two treatment groups using a 2-sided log-rank test, stratified by the randomization stratification factors. EFS will be tested at an overall alpha level of 0.05, as further described in Section 7.3.3.

The median (and quartiles) duration of EFS and the associated 95% CI for each treatment arm will be estimated using the Kaplan-Meier method and the log-log transformation for the event-free survival function.

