7.3.2.4 Transfusion Independence Rate

Transfusion independence rate is calculated as number of subjects with neither RBC nor platelet transfusion for any period of 8 weeks after the initiation of treatment (or C1D1 visit date for subjects randomized to BSC or randomization for subjects not treated) and up to treatment discontinuation divided by the total number of subjects included in the efficacy analysis. The transfusion independence rate will be compared between the 2 treatment groups using a Cochran Mantel-Haenszel test stratified by the randomization stratification factors at an overall alpha level of 0.05, as further described in Section 7.3.3. In addition, the Mantel-Haenszel weighted difference in transfusion independence rate between the 2 treatment groups and the associated CI will be provided.

The individual RBC and platelet transfusion independence rates will also be presented.

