Subjects who did not receive any study treatment, or who do not have a valid post-treatment (or post C1D1 visit date for BSC) efficacy assessment (ie, no post-treatment BM/PB sample or the quality of BM/PB sample is not adequate for an assessment of efficacy) will be classified as not evaluable (NE) for response classifications. These subjects will be included in the denominator of the ITT analysis for calculation of response rates. Subjects who cannot be classified into a response category (CR, CRp, CRi, CRh, or PR) or into the NE category will be classified as non-responders (NR) for a given evaluation time point. For subjects who experience different response levels at different visits, the best response in the order of CR, CRp, CRi, and PR will be used for summary and analyses. Subjects who progress (see Section 7.3.2.1 for definition) prior to experiencing a response (CR, CRp, CRi, CRh, or PR) will be included in the NR category. The best response (CR, CRp, CRi, PR, NR, or NE) based on the investigators will be summarized in a table displaying the number and percentage of subjects who meet the criteria for each endpoint. CRh, which is a subcategory of CRp and Cri, will be summarized similarly.

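### SAP EFS scores the two arms of the best supportive care stratum on different events; the net direction for pooled EFS is unknown

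*SAP*

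**What the plan says.** Protocol 11.6.2.1 defines EFS as time to the "earliest of disease progression, treatment discontinuation, start of alternative anti-leukemia therapy (except for HCT), or death". SAP 7.3.2.1 replaces this with the "earliest of treatment discontinuation (for reasons other than initiation of HCT), start of alternative anti-leukemia therapy (other than HCT), or death", so progression is no longer listed. SAP 1.0 gives the SAP precedence on analysis: "The analyses specified in this document supersede the high-level analysis plan described in the protocol".

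Protocol 5.4.1 governs when treatment ends. For subjects in general, "Investigators can discontinue subjects from study treatment in case of unacceptable toxicity, non-compliance, disease progression requiring alternative therapy"; the subject's best interest is a further ground. For one group it adds: "Subjects in the BSC group will be considered to be on study treatment until they have disease progression".

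For subjects not in response, Protocol 11.6.2.1 defines progression as the point "when PB or BM shows evidence of continued increase in blasts % that necessitates alternative therapy". The SAP has no definition of its own. SAP 7.3.2.5 nevertheless refers to "Subjects who progress (see Section 7.3.2.1 for definition) prior to experiencing a response", and the section it points to contains none.

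The SAP does adapt other rules to BSC. In SAP 7.3.2.4 the transfusion window starts at the initiation of treatment, "or C1D1 visit date for subjects randomized to BSC or randomization for subjects not treated". SAP 7.3.2.5, 7.4.2 and 7.4.4 have similar provisions. SAP 7.3.2.1 has none.

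**The concern.** Preselected TC option is a randomization stratum, so guadecitabine subjects preselected for BSC are compared with BSC controls. One side has a drug to stop and the other does not. Because stopping is itself an EFS event, part of the comparison in this stratum is time to stopping a drug against time to progression or death. Equal disease control could then appear as a treatment difference.

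EFS is the first gated secondary endpoint (SAP 7.3.3). SAP 7.0 also permits comparisons of guadecitabine within each preselected TC option, where any effect in the BSC stratum would be undiluted. The study is open-label and the sponsor is not blinded (Protocol 6.2), so the scoring rule should not be left until the data are final.

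**Working it through.** **Plan's own figures.** The documents size the trial on OS only: 315 deaths for 90% power at a hazard ratio (HR) of 0.692 (SAP 4.0). The Schoenfeld formula gives 311 and the Freedman formula 318, so that figure reproduces. It has no bearing on EFS, for which no figure is stated.

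**Events set side by side in the BSC stratum**, reading SAP 7.3.2.1 with Protocol 5.4.1:

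| Occurrence | Guadecitabine | BSC control |
|---|---|---|
| Death | event | event |
| Alternative therapy other than HCT | event | event |
| Stop for toxicity, non-compliance or investigator decision | event | no counterpart |
| Progression with treatment continued | no event | event, because it ends the BSC treatment period |

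The third row works against guadecitabine and the fourth in its favour.

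**Size within the stratum, no true effect.** Let λ be the hazard of progression, alternative therapy or death, equal in both arms, and δ the hazard of non-progression stops on guadecitabine. Let f = δ/(λ+δ), the share of guadecitabine first events that are such stops. Then HR = (λ+δ)/λ = 1/(1−f).

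If a share g of λ goes unscored on guadecitabine because treatment continues past progression, HR ≈ (1−g) + f/(1−f). The two effects cancel at g = f/(1−f). This probably overstates the offset, because a later stop, therapy or death is still scored.

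**Effect on the pooled test from this stratum alone.** With w the BSC share of EFS events, pooled HR ≈ exp(w × ln[1/(1−f)]).

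The documents give none of f, g or w; all are assumptions.

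| f | BSC-stratum HR (g = 0) | g at which effects cancel | Pooled HR, w = 5% | w = 10% | w = 20% |
|---|---|---|---|---|---|
| 5% | 1.053 | 5.3% | 1.003 | 1.005 | 1.010 |
| 10% | 1.111 | 11.1% | 1.005 | 1.011 | 1.021 |
| 20% | 1.250 | 25.0% | 1.011 | 1.023 | 1.046 |
| 30% | 1.429 | 42.9% | 1.018 | 1.036 | 1.074 |

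To put f on a rate scale, assume a 3-month median for the common events, so λ = ln 2/3 = 0.231 per month. Then f = 10% means 0.231 × 0.10/0.90 = 0.026 stops per month, and f = 30% means 0.231 × 0.30/0.70 = 0.099.

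**Opposing pull from other strata.** Guadecitabine is open-ended (Protocol 7.1.2), while TC duration follows labels and local practice (SAP 3.1). Suppose completing a TC course is scored as discontinuation. Let v be the share of EFS events in strata with finite courses, and q the share of TC first events there that are completions. Then pooled HR ≈ exp(w × ln[1/(1−f)] + v × ln[1−q]).

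Example with w = 10%, f = 10%, v = 40%, q = 20%: exp(0.10 × 0.105 − 0.40 × 0.223) = exp(−0.079) = 0.92.

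Over w = 5% to 20%, f = 10% to 20%, v = 20% to 40% and q = 10% to 30%, the result runs from 0.87 to 1.02, mostly below 1. The sign therefore depends on a rule the SAP does not state and on shares the documents do not give.

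**The case against.** A reader might infer that EFS as a whole is biased against guadecitabine. The documents do not support that. Guadecitabine progression without a stop goes unscored under the SAP, and Table 5 in Protocol 7.3.1 provides for dosing on schedule with peripheral blasts present. Completed TC courses could pull the pooled result the other way. Protocol 7.2 suggests that completion is not a discontinuation, since it ties discontinuation to the addition of a new therapy afterwards, but it is not an EFS rule. Protocol 2.2 reports that few Phase 2 subjects stopped for adverse events. No number is given and other reasons are not covered, but the lower values of f deserve weight.

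The BSC sentence in Protocol 5.4.1 can also be read narrowly. It follows the rules on collecting adverse events and concomitant medications, does not mention EFS, and the list of stopping reasons makes no exception for BSC. On that reading a BSC discontinuation is undefined for EFS rather than confined to progression. This stands as a reading, but the SAP still has no rule for BSC.

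Stopping an active drug for toxicity can legitimately count in a treatment-failure composite, and the protocol always counted discontinuation. This also stands, and it argues for keeping the composite as the main EFS and adding a like-for-like analysis beside it.

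Finally, the consequence is limited. EFS is formally tested only after a significant OS result in favour of guadecitabine, and the DMC found superiority on OS unlikely.

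**Conclusion.** The point holds for the BSC stratum. Followed as written, the two documents let its arms reach EFS through different events, and the SAP leaves this unaddressed although it adapts several other rules to BSC. Within that stratum a disadvantage to guadecitabine is the more likely direction. The protocol ties non-responder progression to a need for alternative therapy, so few progressions should go unscored on guadecitabine. The illustrative null HR is 1.05 to 1.43 for f between 5% and 30% with g = 0. It would reverse if g exceeded f/(1−f).

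For pooled EFS no direction can be claimed. The BSC stratum alone would move the HR by about 0.3% to 7% over the assumed ranges, and the treatment of completed TC courses could outweigh that. OS is unaffected.

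Restoring progression as an event is necessary but not sufficient. It sets g to zero and so removes the offset, but non-progression stops would still count on one side only.

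**What to change.** Before the final database lock, which SAP 6.0 describes as still to come:

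- Put the progression event and definition from Protocol 11.6.2.1 into SAP 7.3.2.1, where SAP 7.3.2.5 already points.
- State there that, for EFS, BSC discontinuation is dated at progression, and that completing a planned TC course is not in itself an event.
- Pre-specify one EFS sensitivity analysis with the same event list in both arms and all strata: progression or relapse, alternative anti-leukemia therapy except HCT, or death. Discontinuation counts only when its recorded reason is progression.
- Show EFS by preselected TC option.

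The main test should not use a separate event rule for the BSC stratum alone. EFS would then mean different things in strata pooled into one log-rank test, and unfavourable guadecitabine events would be removed from one stratum only.

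The cost is SAP wording and one extra analysis. Protocol 5.4.1 already requires the discontinuation reason on the CRF, and Protocol 9.5.6 continues response assessment after an early stop. The downside is that toxicity stops do not count in the sensitivity analysis, though they remain in the main EFS and in the adverse event and disposition tables. One limit remains: a BSC subject for whom no further therapy is intended may never meet the protocol's non-responder definition. The display by TC option would help to show whether this matters.

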7.3.2.2 Survival Rate at One-Year and Two-Years

One-year survival rate is defined as the survival rate at the end of the first year from randomization. One-year survival rate for each treatment group will be estimated by Kaplan-Meier procedure as addressed in Section 7.3.1. Hypothesis testing will be based on the stratified Kaplan-Meier estimates and standard errors estimated by the Greenwood formula using the log-log transformation of the OS function at an overall alpha level of 0.05, as further described in Section 7.3.3. Subjects who do not have death in record will be censored on the last date known to be alive. The stratification factors will be the same as those used in the OS analysis.

The survival rate at 2 years will be similarly summarized.

7.3.2.3 Number of Days Alive and Out of the Hospital

The date of each hospital admission and discharge were collected for each subject for at least 6 months (and until disease progression for subjects who had not progressed during the first 6 months or until the subject died or withdrew consent prior).

The duration of each individual hospital stay in days (regardless of the reason for hospitalization) is calculated as:

Duration of individual hospital stay = date of discharge – date of admission

For a subject who was admitted and discharged on the same day, the duration of hospital stay will be 0. The total duration of all hospital stays in the first 6 months is the sum of the durations of all individual hospital stays occurring between date of randomization and Day 180. For ease of calculation, one month is defined as 30 days for analyses conducted in this study.

The NDAOH within the first 6-month period is calculated as:

NDAOH6M = 180 - total duration of all hospital stays - number of death days before Day 180

For subjects who died within the first 6-month period, the number of death days before Day 180 is calculated as:

Number of death days = (date of Day 180 - date of death)

For subjects who died on or after Day 180 the number of death days before Day 180 will be set to 0.

For subjects who were lost to follow-up within 6 months (expected to be a very small number), the NDAOH will be calculated conservatively assuming that the subject would have died the day after the last contact day.

The NDAOH6M will be summarized by treatment group and comparisons between the 2 treatment groups will be performed using an analysis of variance (ANOVA) model at an overall alpha level

of 0.05, as further described in Section 7.3.3. The variables used for stratification at randomization will be included in the analysis of variance model as fixed factors.

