6.1 Randomization

Eligible subjects will be randomly assigned to study treatment. Treatment assignments for the individual subjects will be determined through a computer generated randomization scheme and accessed through an interactive response system. Instructions for access and use of the interactive response system for randomization will be provided to participating study centers separately.

Randomization will be 1:1 between guadecitabine and TC groups, and will be stratified by intensity of preselected TC option (high intensity vs low intensity vs BSC), ECOG performance status (0-1 vs 2), baseline cytogenetics (poor risk vs other; see Appendix 3), and study center region (North America vs ROW).

Selection of 1 of the TCs must be made prior to the randomization of each subject. Subjects should receive study treatment as soon as possible after randomization (maximum of 1 week between randomization and treatment).

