BM aspirate or biopsy: BM aspirate and/or biopsy differential count will be performed according to local standard practice. The screening aspirate must be collected within 28 days before starting study treatment. A biopsy should be done if no spicules are observed in the aspirate. Repeat the BM sample if not interpretable.

Perform BM aspirate/biopsy at screening and then at the end of Cycles 1, 3, and 6 (ie, on or at any time prior to Day 1 of Cycles 2, 4, and 7), unless PB shows persistence of \geq 5% leukemic blasts that excludes the possibility of a marrow response. Subjects who discontinue treatment before Cycle 6 Day 1 and before documented disease progression must undergo monthly response assessment until 6 months after the start of study treatment or until disease progression or relapse is confirmed, whichever is first. After Cycle 6, repeat BM aspirate/biopsy every 3 months for the first year on study; BM will be repeated every 6 months thereafter until PB or BM assessment shows disease progression or relapse.

- ^s Hospitalizations/Transfusions: Document all blood and platelet transfusions (blood product transfused and units) within 56 days before starting study treatment. Document all hospital admission and discharge dates and main reason for hospitalization, as well as all blood and platelet transfusions (blood product transfused and units), from Cycle 1 Day 1 and then monthly to 6 months after the first dose, then at every study visit until disease progression.
- ^t **Disease progression status:** For subjects who discontinue study treatment before disease progression is documented, PB and BM aspirate/biopsy assessments as described in footnote "r" should continue until disease progression or relapse is confirmed.

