9.5.2 Screening and Baseline Procedures

After the investigator or sub-investigator confirms that a subject is eligible and willing to participate in the study, study center personnel will forward the appropriate documentation to the attention of the sponsor according to the Study Procedures Manual.

Bone marrow aspirate/biopsy samples may be collected within 28 days before Cycle 1 Day 1. Within 14 days before randomization, perform the following study procedures and tests:

- Written informed consent. The ICF must be signed and dated by the subjects before any study-specific samples are collected or study-specific procedures are initiated.
- Complete medical history, including demographics. Record disease history, including the date of initial diagnosis. Document concurrent medical signs and symptoms to establish baseline conditions.
- Record prior anti-leukemic therapies, including start and stop dates, best response and duration of response.
- Record all medications taken within 14 days before randomization.
- Complete physical exam including height and weight, and examination of body systems according to institutional standards.
- Vital signs include resting systolic/diastolic blood pressure, resting respiration rate, resting heart rate, and body temperature.
- Serum or urine pregnancy test: for women of child-bearing potential only. Results must be negative for the subject to be eligible for enrollment into the study.
- ECOG performance status (Appendix 1).
- Height measurement (for BSA calculation).
- All study-procedure-related AEs from the time of informed consent.
- Blood and urine sample collection for clinical laboratory tests (Table 8).
- •
- Adequate BM aspirate slide or biopsy to include touch prep slide, collected within 28 days before starting study treatment.
- Cytogenetic assessments performed at any time before randomization.
- Document all blood and platelet transfusions (blood product transfused and units) performed within 56 days before randomization.
- Investigator's confirmation of eligibility. Perform all necessary procedures and evaluations to document that the subject meets each eligibility criterion.

• Study treatment randomization, after eligibility is confirmed. Randomize as close as possible to the first dose of study treatment (on Cycle 1 Day 1). Treatment should start as soon as possible after randomization, and in all cases within 1 week.

Table 8:Clinical Laboratory Tests

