9.5.3.1 Day 1 (Before Dosing), Cycles 1-3

- Complete physical examination (does not need to be repeated if was done ≤4 days before Cycle 1 Day 1).
- Vital signs.
- ECOG performance status (Appendix 1).
- 12-lead ECG (triplicate) (rhythm, atrial rate, ventricular rate, PR interval, QRS duration, and QT/QTc, morphology and overall interpretation), Cycle 1 only.

- Health-related QOL (Appendix 2).
- Weight and BSA calculation (use height from screening; BSA recalculation is only required if weight changes ±10% or more from last calculation).
- Cycle 1: All study-procedure-related AEs and concomitant medications.
- Cycles 2-3: All AEs and concomitant medications.
- Sample collection for laboratory assessments, including:
 - Hematology (see Table 8) (does not need to be repeated if done \leq 4 days before Day 1).
 - Serum chemistry (see Table 8) (does not need to be repeated if done \leq 4 days before Day 1).
 - Serum or urine pregnancy test for women of child-bearing potential only (for Cycle 1 Day 1 does not need to be repeated if done at screening within 7 days of C1D1).
- BM aspirate/biopsy required at the end of Cycle 1 (ie, Day 1 of Cycle 2) unless PB shows persistence of \geq 5% leukemic blasts that excludes the possibility of a marrow response.

•

• Hospital admission and discharge dates (and the main reason for hospitalization), as well as all blood and platelet transfusions (blood product transfused and units) since Day 1 of previous cycle.

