5.0 ANALYSIS SETS

5.1 Efficacy Analysis Set

Efficacy analyses will be based on intent-to-treat (ITT) principle. The Efficacy Analysis Set will include data from all subjects randomly assigned to study treatment. All data will be included and no subjects excluded because of protocol violations. For the analysis of efficacy data, subjects will be included in the treatment group according to their randomly assigned treatment.

For NDAOH, and health-related QOL by EQ-5D-5L, the primary analysis will include only the data collected during the first 6 months of the study because, during this study period, subjects are assessed monthly whether or not they are still on study treatment. Secondary analysis, if performed, may also include data beyond the first 6 months of the study (eg, over the entire study period until disease progression).

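### NDAOH counts hospital days from randomization, but hospital dates are collected from Cycle 1 Day 1 and stays are not cut at the window edges

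*SAP*

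**What the plan says.** SAP 7.3.2.3 takes a fixed 180 days, subtracts the total duration of hospital stays, and subtracts the days from death to Day 180. The stays to be summed are "all individual hospital stays occurring between date of randomization and Day 180". The length of each stay is its discharge date minus its admission date. A subject lost to follow-up is treated as having died the day after last contact.

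The subjects scored are all those randomized. SAP 5.1: "The Efficacy Analysis Set will include data from all subjects randomly assigned to study treatment".

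Collection is described in protocol Table 7, footnote s: "Document all hospital admission and discharge dates and main reason for hospitalization", and this runs "from Cycle 1 Day 1 and then monthly to 6 months after the first dose". Before treatment, the screening list in protocol 9.5.2 asks for transfusions ("Document all blood and platelet transfusions (blood product transfused and units) performed within 56 days before randomization") and has no item for hospital stays. The pre-dose Day 1 list in protocol 9.5.3.1 looks back to Day 1 of the preceding cycle.

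Protocol 6.1 allows a "maximum of 1 week between randomization and treatment". Footnote f to Table 7 lets the two fall on the same day.

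**The concern.** The endpoint's clock starts at randomization and the hospital record starts at C1D1. The formula works by subtraction from 180, so a day on which a subject is alive and no hospital stay is on file counts as a good day. A missing record is not neutral: it improves the score. SAP 7.8 plans no imputation except as specified, so nothing later corrects it.

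Subjects randomized but never treated have no C1D1 and no first dose. The collection window in footnote s therefore has no start for them, yet they are in the analysis. Long-term follow-up (protocol 9.5.6) does not supply one: it begins after treatment is discontinued, and its monthly phase is counted from the start of treatment. The SAP provides for these subjects in the baseline definition (7.0), transfusion independence (7.3.2.4) and response (7.3.2.5), but not in NDAOH.

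A second defect is independent of collection. The SAP does not say how to treat a stay that begins before randomization or ends after Day 180.

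NDAOH is third among the gatekept secondary endpoints (SAP 7.3.3) and is also to be summarized by arm, so the values need to be right even if it is never formally tested.

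**Working it through.** The documents give no expected value, standard deviation or power for NDAOH, so there is no planned figure to reproduce. The check applies the SAP formula with and without the days in question.

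**Inputs**
- Score = 180 − H − D, where H is recorded hospital days and D is days from death to Day 180 (SAP 7.3.2.3).
- Gap from randomization to C1D1: 0 to 7 days (protocol 6.1; Table 7, footnote f).
- Day t means t days after randomization.

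**1. Does another passage fill the gap before C1D1?** The screening list asks for transfusions only. The Day 1 look-back has no preceding cycle to refer to in Cycle 1. The screening column of Table 7 has a mark in the combined hospitalizations/transfusions row, but footnote s gives that row only transfusions as pre-treatment content. No passage clearly fills it.

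**2. Treated subject, in hospital for a full 7-day gap, discharged by C1D1, no other stays, alive at Day 180**
- True score: 180 − 7 − 0 = 173.
- Score if the stay is unrecorded: 180 − 0 − 0 = 180.
- Error: 7 days, and 7/180 = 3.9%. This is the maximum; it is zero if randomization is on C1D1.

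**3. Never-treated subject, no stays recorded**

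| Case | Computed | True |
|---|---|---|
| Alive at Day 180, 10 hospital days | 180 | 180 − 10 = 170 |
| Alive at Day 180, 30 hospital days | 180 | 180 − 30 = 150 |
| Alive at Day 180, 60 hospital days | 180 | 180 − 60 = 120 |
| Died Day 20, in hospital throughout (D = 180 − 20 = 160) | 180 − 0 − 160 = 20 | 180 − 20 − 160 = 0 |

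A subject lost at randomization counts as dead on Day 1, so D = 179 and the score is 180 − 179 = 1. The death and loss rules therefore bound the excess credit: it cannot exceed the days the subject was alive and in follow-up. The hospital-day counts in the table are illustrative; the documents give none.

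**4. Stay crossing Day 180 (Day 170 to Day 200)**
- Days inside the window: 180 − 170 = 10.
- Counted whole, as discharge minus admission: 200 − 170 = 30, which over-subtracts by 20.
- Excluded because it does not lie wholly inside the window: 0, which under-subtracts by 10.

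Two programmers following the same text could differ by 30 days for one subject. The same holds at the start: a stay begun a days before randomization and ended b days after it should subtract b, but the stated duration is a + b.

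**5. Effect on an arm mean.** This equals the share of subjects affected times the mean error per affected subject. The documents give neither term for either arm, so no arm-level figure or sign can be computed.

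**The case against.** The strongest reply is that footnote s can be read as a visit schedule for recording rather than a bar on earlier dates. SAP 7.3.2.3 says that dates were collected for each subject for at least six months. Protocol 9.1 says that all admissions will be documented and used for NDAOH. SAP 5.1 says that subjects are assessed monthly whether or not they remain on treatment. Sites may well have entered the missing stays. This shows that the record may be fuller than footnote s implies. But none of these statements gives a start date, and being assessed after stopping treatment does not cover a subject who never started.

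Several stronger readings are tempting, and the documents do not support them:
- *Every hospital day in the gap is lost, including for subjects admitted early for in-patient chemotherapy.* A stay still open on C1D1 would normally be entered with its true admission date, and its gap days would then be counted. For treated subjects the loss is clear only for stays that ended before C1D1.
- *Never-treated subjects are credited with all their hospital days.* That requires the subject to stay alive and in follow-up while the site records nothing.
- *The arm with more untreated or early-admitted subjects gains days.* The number never treated and the gap by arm are not given. Uncut stays counted whole pull the score down, opposite to unrecorded stays. Neither the net sign nor the size of a difference between arms can be derived.
- *A formal test is at risk.* NDAOH is tested only if OS, EFS and one-year survival are each significant in favor of guadecitabine, and the DMC had already judged superiority on OS unlikely.

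**Conclusion.** The point holds as a mismatch between the counting window and the collection window, together with a missing rule for cutting stays. For a treated subject, unrecorded gap stays can add at most 7 of 180 days (3.9%), and often nothing, since randomization is meant to be close to C1D1. For a never-treated subject the excess equals the unrecorded hospital days while alive and in follow-up. The edge problem can be larger for one subject, 20 days too many or 10 too few in the worked stay, and can arise in either arm.

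These conclusions rest on reading footnote s literally for stays that ended before C1D1 and for never-treated subjects, and on the SAP formula being programmed as written. Any between-arm effect is undetermined in size and direction. The consequence is mainly for the reported NDAOH summary. It is still worth correcting, because the SAP's stated rule can yield wrong values and the final database lock was still ahead when the SAP was written (SAP 6.0).

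**What to change.** 1. In SAP 7.3.2.3, count only hospital days between randomization and Day 180, clipping stays at both ends: days per stay = max(0, min(discharge, Day 180) − max(admission, randomization)).
2. Before the final lock, issue one data query for stays between randomization and C1D1, and for all stays in the first 180 days of never-treated subjects. Ask sites to confirm explicitly where there were none, so that no stay can be told apart from no information.
3. State in the SAP how never-treated subjects with no hospital record are scored, and add a sensitivity analysis for them. A simple pair of bounds is to score their days alive in the window first as all out of hospital and then as all in hospital.

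Amending footnote s would achieve nothing now: enrollment closed in September 2018, so every subject's first 180 days had passed before the January 2020 cutoff. Restarting the 180 days at C1D1 is not a substitute, because it moves the origin to a post-randomization event and does not recover the stays of untreated subjects.

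The cost is a few lines of SAP text and some site effort on dates that should be in source records. A few dates may stay missing, which the third item covers for never-treated subjects.
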